4 STATISTICAL ANALYSES

4.1 Sample size of analysed sets

The objective of analysis presented below is to describe analysis populations.

Criteria	Number of subjects in the Randomized Set (RS) Number of subjects in the Safety Set (SS) Reasons of exclusion from SS
	Number of subjects in the pharmacokinetic set (PKS) Reasons of exclusion from the PKS
	Number of subjects in the pharmacodynamics set (PDS) Reasons of exclusion from PDS
Statistical method	Descriptive statistics by dose group and overall.
Title of table	Sample size of analysed sets by dose group and overall.

4.2 Demographic characteristics

The objective of analysis presented below is to describe the demographic and baseline characteristics.

Demography

Criteria	Age (years) Gender (Male/Female) If Female, is she infertile or in post-menopause for at least 2 years? (yes/no) Weight (kg) Height (cm) BMI (kg/m ²)
Populations	RS and PKS/PDS/SS Sets (in case different from the RS).
Statistical method	Descriptive statistics.
Title of table	Demographic characteristics by dose group and overall.

Medical and surgical history

Criteria	System Organ Class (SOC), MedDRA dictionary Preferred Term (PT), MedDRA dictionary
Information	All history events will be coded using the Medical Dictionary for Regulatory Activities (MedDRA) dictionary.
Populations	RS.
Statistical method	Descriptive statistics as subject count by SOC and PT. Listing of medical history events by dose group and subject.
Title of table	Number and percentage of medical and surgical history events by SOC and PT by dose group and overall. Listing of medical and surgical history by dose group and

	subject.
--	----------

Previous medications

Criteria	ATC term, Who Drug dictionary preferred name term, Who Drug dictionary
Populations	RS.
Statistical method	Descriptive statistics. A listing will be performed by subject.
Title of table	Number and percentage of previous medications by ATC term and preferred name term by dose group and overall. Listing of previous medications by dose group and subject.

Physical examination at screening and D-1

Criteria	For each examination: assessment (normal/abnormal) and clinically significant (yes/no) At screening Skin and mucous Ear/nose/throat Pulmonary Cardiac Gastro-intestinal Neurological
Information	Result and clinically significant will be summarised in one 3-class criterion (normal/abnormal NCS/abnormal CS).
Populations	RS.
Statistical method	Descriptive statistics. If relevant, listing of abnormal findings by subject.
Title of table	Physical examination at screening and D-1 by dose group and overall. If relevant, Listing of abnormal findings by dose group and subject.

Urine drug screen

Criteria	Results (negative/positive/not done)
Information	Urine drug screen criteria are assessed at screening and at D-1. Results concern: Cannabinoids, amphetamines, cocaine, benzodiazepines, opiates and cotinine.
Populations	RS.
Statistical method	Descriptive statistics.
Title of table	Urine drug screen at screening and at D-1 by dose group and overall.

Alcohol breath test

Criterion	Result (negative/positive)
Information	Alcohol breath test performed at screening and at D-1.
Populations	RS.
Statistical method	Descriptive statistics.
Title of table	Alcohol breath test at screening and at D-1 by dose group and overall.

Serology

Criteria	HIV1 and 2 antibodies (negative/positive/not done) HCV antibodies (negative/positive/not done) HBs antigen (negative/positive/not done)
Information	Serology criteria are assessed at screening.
Populations	RS.
Statistical method	Descriptive statistics.
Title of table	Serology at screening by dose group and overall.

4.3 Pharmacokinetics and pharmacodynamics analyses

Criteria	Cmax (ng/mL); tmax (h); λZ ; $t_{1/2}(h)$; AUC ₀₋₂₄ (h×ng/mL); AUC _{0-t} (h×ng/mL); AUC _{0-∞} (h×ng/mL); fu VZ/F (DF2577Y only); CL/F (DF2577Y only); $A_{e,ur}$; $f_{e,ur}$ $A_{e,f}$; $f_{e,f}$ CLR; Parent:metabolite(s) ratio for Cmax and AUCs.
Information	Interim analyses will be performed after completion of each dose level, using anonymized data provided by the bioanalytical center Final PK analysis will be performed using validated bioanalytical data and actual PK blood sampling times of the part A of the study
Population	PKS
Statistical method	Descriptive statistics of concentrations and PK parameters Dose proportionality analysis using power model (section 3.3)
Title of tables	List of concentrations Descriptive statistics of concentrations List of PK parameters Descriptive statistics of PK parameters

Pharmacodynamic analysis: correlation between Cmax and pharmacodynamics criteria

Criteria	Pharmacokinetic criterion DF2577Y Cmax (ng/mL) Pharmacodynamic criteria Leukocyte markers: CD11b, CD18
Information	DF2577Y concentration assessed at D1 (pre-dose, T30min, T1h, T2h, T3h, T4h, T5h, T6h, T7h, T8h, T9h, T10h, T11, T12h, T16h), D2 (T24h, T36h, T40h), D3 (T48h, T60h) and D4 (T72h). Leukocytes markers not assessed for first cohort. Leukocytes markers assessed at D1 (Tcmax, Tcmax+3h, T12h), D2 (T24h), D3 (T48h) or D4 (T72h) (time determined after the results of the first dose administered).
Population	PKS
Statistical method	Time matched: D1 (Tcmax, Tcmax+3h, T12h), D2 (T24h), D3 (T48h) or D4 (T72h). The relationship between values of pharmacodynamic parameters time matched with DF2577Y (bound and unbound) plasma concentrations will be first evaluated by visual inspection of graphs relating pharmacodynamic parameters with DF2577Y (bound and unbound) plasma concentrations. In case of reliable relationships, basic models, such as Emax model, will be first developed. Then, the selected models will be optimized by testing covariate such as BMI, age, etc. Further model development might be done depending on the results of each modelling.
Title of tables	Cmax concentration vs CD11b for each time matched. Cmax concentration vs CD18 for each time matched.

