10. STATISTICS

10.1. Description of the statistical methods

The statistical analysis will consist in individual data listings and descriptive statistics performed by EUROFINS OPTIMED, using the SAS® computer program (release 9.3).

All individual data for all included subjects will be presented in data listings, sorted by subject within study product/treatment group.

Demographic and baseline characteristics data will be summarized by product/treatment, cohort and visit day where consistent.

For parameters with evaluation before dosing and in case of rechecked value(s) for one subject, only the last observation will be used in descriptive statistics and derivations of other parameter values. After dosing, only observations planned in the protocol will be used in descriptive statistics.

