10.1.1. Descriptive statistics

Descriptive statistics for quantitative parameters will be provided using mean, Standard Deviation (SD), Standard Error of the Mean (SEM), minimum, median, maximum, and number of observations; descriptive statistics for qualitative parameters will be provided using frequencies (n) and percent frequencies (%). Percent will be calculated using as denominator the actual number of non-missing data.

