1 INTRODUCTION

In accordance with the main characteristics of the protocol, the Statistical Analysis Plan (SAP) details that the scheduled analyses are to be performed in order to evaluate the tolerability and safety of ascending single and repeated doses of DF2755A in healthy adult male and female volunteers.

Study design

The study is a phase I, single center, double-blind, placebo controlled, randomized, ascending single and repeated doses study in healthy male and female volunteers.

The design consists of a double blind comparison of the test compound versus placebo in which the dose is increased in successive treatment periods.

The Multiple Ascending Dose (MAD) will be initiated only after the authorization, from ANSM of a substantial amendment that will be presented in order to notify the results of Single Ascending Dose (SAD) part of the study. Besides in order to decide to move forward from SAD to MAD, the pharmacokinetic data for all doses administered during SAD will be evaluated (i.e. plasma: quantitative determination of DF2755A bound and unbound; qualitative and preliminary quantitative determination of known metabolites; urine and faeces: qualitative and quantitative determination of parent compound and qualitative and preliminary quantitative investigation of known metabolites).

Dose will be escalated in order to achieve enough safety information on an interval of doses possibly encompassing both the effective dose and the maximum tolerated dose (defined as the highest dose devoid of any clinical signs/symptoms).

Part A: Single doses of 50 mg oad, 150 mg oad, 450 mg oad or 700 mg oad of DF2755A are planned to be tested in healthy male and female volunteers.

Objectives of the study

Primary objectives

- To evaluate the tolerability and safety of ascending single and repeated doses of DF2755A in healthy adult male and female volunteers.

Secondary objectives

- To determine the pharmacokinetics parameters of DF2755A.
- To establish a dose concentration-response relationship over a wide range of doses in order to select a narrower range of dose and dosing regimen to be subsequently studied in patients after single and multiple administration.
- To evaluate the effect of ascending single and repeated doses on the pharmacodynamics parameters.
- To compare metabolites pathway in Human with the one observed in animals.

Criteria for evaluation

Primary evaluation criteria:

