3.2 Descriptive statistics

At least the following descriptive statistics will be reported:

- *Continuous variables*: Number of observations (N), mean, standard deviation (SD), standard error of the mean (SEM) minimum (Min), median and maximum (Max).
- *Categorical variables*: Frequency (n) and percentage (%).

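### For Part A, SAP 4.3 plans only an exposure-PD relationship: the dose-effect PD objective gets no CD11b/CD18 result by dose, and the block conflicts on exposure metric, sampling times and population

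*SAP*

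**What the plan says.** SAP Section 1 has two distinct PD-related secondary objectives. One is a dose concentration-response relationship. The other is "To evaluate the effect of ascending single and repeated doses on the pharmacodynamics parameters".

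SAP 4.3 contains one PD block, "Pharmacodynamic analysis: correlation between Cmax and pharmacodynamics criteria".

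- **Method:** graphs of PD values against time-matched bound and unbound concentrations, then Emax-type models if a reliable relationship is seen. Protocol 10.1.1.2 has the same method.
- **Tables:** two titles, "Cmax concentration vs CD11b for each time matched" and its CD18 counterpart.
- **Sampling times:** "Leukocytes markers assessed at D1 (Tcmax, Tcmax+3h, T12h), D2 (T24h), D3 (T48h) or D4 (T72h").
- **Population:** the pharmacokinetic set (PKS). SAP 2.4 also defines a pharmacodynamic set (PDS), and SAP 4.1 reports "Number of subjects in the pharmacodynamics set (PDS) Reasons of exclusion from PDS".

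General rules exist. Protocol 10.1.1 states "Descriptive statistics for quantitative parameters will be provided using mean, Standard Deviation (SD") and further statistics. SAP 3.2 states "At least the following descriptive statistics will be reported" and gives the list for continuous and categorical variables. Protocol 10.1 adds "All individual data for all included subjects will be presented in data listings".

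**The concern.** The exposure-response graphs and models answer one objective and leave the other without a defined output. If no reliable relationship is seen, the PD part of the report would consist of graphs, with no summary of either marker at 150, 450 or 700 mg.

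The inconsistencies inside 4.3 also matter. A programmer who follows the table titles produces a different analysis from one who follows the method row. Both would work from a list of CD times without the baseline sample, and on a population chosen for PK. A programmer who follows Section 5 would list markers that Part A does not measure and omit those it does. Choices left open here could end up being made after the data are seen.

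**Working it through.** **1. Sample counts.** Protocol 7.2 (Part A) schedules six CD11b/CD18 samples: pre-dose, Tcmax, Tcmax + 3 h, T12h, T24h, and T48h or T72h. Protocol 8.2.3 confirms this:

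- cohort 1: 18.7 + 30.6 + 120 = 169.3 mL
- cohorts 2 to 4: 169.3 + 6 × 6 = 205.3 mL, as stated.

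SAP 4.3 lists five times, and the missing one is pre-dose. PD sampling starts with the second cohort, so full enrolment gives 3 × 8 = 24 subjects (18 active, 6 placebo). Planned samples are 24 × 6 = 144. The times in 4.3 cover 24 × 5 = 120. The 24 pre-dose samples are left out.

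**2. Baseline and change, by domain in the SAP.**

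| Domain | Baseline | Change from baseline |
|---|---|---|
| Laboratory (4.5) | D-1 | yes |
| Vital signs (4.6) | D1 pre-dose | yes |
| Weight (4.6) | D-1 | yes |
| ECG (4.8) | D1 pre-dose | yes |
| CD11b/CD18 (4.3) | none | none |

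The general rules in Protocol 10.1.1 and SAP 3.2 name statistics. They name no PD variable and no PD baseline. SAP 3.3 covers safety and PK only.

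**3. Exposure metric.** Cmax is one value per subject, so the table titles pair the same x-value with five CD times. The method row pairs five concentrations with five CD times. The two can agree only at the Tcmax sample, and only approximately, because Protocol 7.2 fixes that time from the first-dose results and not from each subject's own peak.

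**4. Population.** PKS excludes subjects with major deviations affecting PK; PDS excludes those with deviations affecting PD. With PKS, a subject with valid CD data but a PK deviation is dropped, and one with only a PD deviation is kept. The PDS is counted but is the population for no PD analysis.

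**5. Listing.** Under its PD criteria, SAP Section 5 names CXCL1, CXCL2, CXCL5, CXCL6 and CXCL8. Protocol 3.1.2 and Section 7 assign these to Part B only. CD11b and CD18 do not appear, which conflicts with the all-data listing rule in Protocol 10.1. Reactive oxygen species (ROS) is a PD criterion in SAP Section 1 but is neither analysed in 4.3 nor listed in Section 5.

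**6. Precision of a by-dose table.** For 6 active versus 6 pooled placebo, the unadjusted 95% half-width in SD units is t × √(1/6 + 1/6) = t × 0.577:

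- two groups only, 10 df: 2.228 × 0.577 = 1.29
- SD pooled over four groups of 6, 20 df: 2.086 × 0.577 = 1.20.

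**The case against.** The general descriptive rules arguably already authorise a CD11b/CD18 summary, and SAP 3.1 carries over the protocol's methods. The pre-dose sample is collected whatever 4.3 says, and both documents describe the method as time-matched, so Cmax could be read as a labelling slip. All of that is fair, and it limits the point to an unspecified table and baseline plus conflicting text; no data are missing. The contrast with the safety sections holds for baseline only, since those tables too are by dose group and overall, with no stated placebo comparison.

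A reader might infer more than the documents support:

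- **That there is no zero-dose reference.** The late sample may supply one within subject. With the 8 h upper end of the 3 to 8 h animal half-lives in Protocol 1.2.1.3, and a 2 h tmax (both assumptions for humans), T48h would be 2^(-46/8) = 1.9% of Cmax. At the 19.9 h seen in one rat group it would be 2^(-46/19.9) = 20%. What is missing is a defined baseline and control for time effects.
- **That placebo samples are unused.** Adding the 6 × 5 = 30 post-dose placebo samples to the 24 pre-dose ones would give 54. But 4.3 does not exclude placebo, and Protocol 3.7.1 keeps the analytical centre blinded. Whether placebo subjects enter the PKS is unclear. Only the 24 are firm.
- **That the Cmax titles bias EC50 by a known factor.** Cmax over the T24h concentration is 2^(22/half-life), with tmax again taken as 2 h. Across the reported animal half-lives of 1.62 to 19.9 h this runs from about 2 to about 12,000. With one half-life common to all subjects, Cmax would merely rescale the axis. No useful figure follows.

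**Conclusion.** The point holds. The dose-effect PD objective has no specified CD11b/CD18 result by dose, and 4.3 conflicts with its own method, with the protocol's sampling schedule and with the SAP's own PD population. The Section 5 listing is wrong for Part A. This goes beyond missing detail, because following the titles and listing literally gives the wrong output.

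The firm count is 24 omitted pre-dose samples out of 144, assuming full enrolment of cohorts 2 to 4. The rest rests on comparing the texts and needs no assumption about human kinetics or marker variability. The consequence is confined to a secondary, descriptive objective.

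**What to change.** 1. Add to SAP 4.3 a descriptive table on the PDS of CD11b and CD18 (and ROS if assayed): observed value and change from D1 pre-dose at each time, by dose and pooled placebo. Label it descriptive and note that pooling placebo does not remove cohort differences. Adjust any estimated dose-versus-placebo difference for the pre-dose value.
2. Add pre-dose to the CD times in 4.3.
3. Use the concurrent concentration throughout the PK-PD step and retitle the heading and tables to match. Pre-dose concentrations follow the existing below-LOQ rule (Protocol 6.1, SAP 3.3). State that placebo records enter at zero concentration.
4. In Section 5, replace the Part A cytokine listing by CD11b and CD18 (and ROS if assayed).

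The cost is SAP wording and a few extra tables from blood already scheduled. The drawback is that the by-dose contrasts will be too imprecise to read as more than descriptive.

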5.3. Medication(s)/treatment(s) permitted and no permitted before and/or during the trial

No concomitant therapy (prescribed or non-prescribed drug included OTC) will be allowed during the study, except paracetamol (maximum 500mg per administration, total daily dose maximum 2g). However, in case of intercurrent illness or emergency, the investigator is allowed to use any needed medication.

This must be done with a particular attention to the available pharmacological knowledge of the given medication and possible interaction(s) with the study drug. In case of intake of any concomitant medication during the study, the following information must be noted in the relevant section of the eCRF:

- Name of the treatment and its form,
- Reasons for prescription,
- Date and time of start,
- Route of administration,
- Daily dose,
- Duration of treatment.

The decision to withdraw the subject may be made by mutual agreement between the Investigator and the Sponsor.

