2.4 Analysis populations

The Randomized set (RS) will be defined as all randomized subjects.

The Safety set (SS) will be defined as all included subjects having taken at least one dose of study drug.

The pharmacokinetic set (PKS) will be defined as all the included subjects who have taken at least one dose of study drug without major protocol deviations affecting pharmacokinetics and with available data.

The pharmacodynamic set (PDS) will be defined as all the included subjects who have taken at least one dose of study drug without major protocol deviations affecting pharmacodynamics and with available data.

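### The SAP's only pharmacodynamic analysis is assigned to the pharmacokinetic set, so the pharmacodynamic set it defines screens no outcome

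*SAP*

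**What the plan says.** SAP 2.4 gives the PKS and the PDS parallel definitions. Both start from included subjects who took at least one dose. The PKS then keeps those "without major protocol deviations affecting pharmacokinetics and with available data", and the PDS keeps those "without major protocol deviations affecting pharmacodynamics and with available data".

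SAP 4.3 holds the plan's single analysis of pharmacodynamic markers in Part A, under the heading "Pharmacodynamic analysis: correlation between Cmax and pharmacodynamics criteria". It plots CD11b and CD18 against time-matched bound and unbound DF2577Y concentrations. If a relationship looks reliable, it goes on to basic models such as Emax, with covariates. The population row of that table is "Population PKS".

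The PDS appears elsewhere in the SAP only in supporting material. Section 4.1 counts it and gives "Reasons of exclusion from PDS". Sections 4.2 (demography) and 4.9 (study duration) describe it where it differs from the randomized set. Section 5 lists membership by subject.

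The protocol defines no pharmacodynamic set. Its section 10.7 says only that subjects given the wrong treatment are analysed by the treatment received.

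**The concern.** A set built to protect the pharmacodynamic data is never applied to them. A programmer working from the population row in SAP 4.3 would select on PK validity alone. The report could then list a subject as excluded from the PDS, with the reason, and still plot that subject's CD11b and CD18 values in the only pharmacodynamic result.

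One secondary objective is a dose- and concentration-response relationship that will narrow the doses and regimens studied in patients. In Part A this table is the only place where the SAP addresses the response side. With six active subjects per dose and a first step done by eye, a single unsuitable profile can change how the graph reads and whether a model is attempted.

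**Working it through.** **Who is kept under each choice.** The two definitions sort treated subjects with available data into four cells:

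| Major deviation affecting PK | Major deviation affecting PD | In PKS | In PDS | In both |
|---|---|---|---|---|
| No | No | Yes | Yes | Yes |
| No | Yes | **Yes** | **No** | No |
| Yes | No | No | Yes | No |
| Yes | Yes | No | No | No |

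An analysis of concentration against marker needs both measurements to be sound, so only the first row belongs. The PKS as named lets in the second row. A plain swap to the PDS would remove that row and let in the third. Only the intersection gives the first row alone.

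**Can the second row occur?** The protocol makes it possible in two ways.
- Leukocyte blood goes into a separate K3 EDTA tube, is kept at 4°C away from light, and is read on a flow cytometer at a hospital immunology laboratory (Protocol 7.2). PK blood goes into lithium heparin, is centrifuged and frozen, and goes to the sponsor's bioanalytical laboratory (Protocol 6.3.1). The first chain can fail while the second stays intact.
- Apart from paracetamol, and outside illness or emergency, concomitant drugs are not allowed (Protocol 5.3). A prohibited anti-inflammatory could be classed as a major deviation affecting pharmacodynamics only.

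In either case the subject falls in the second row only if the event is graded major. Protocol 12.4 provides for that grading by the time of the blind review.

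**Scale.** Inputs: four Part A cohorts of 8, each with 6 active and 2 placebo (Protocol 1.6), and "Leukocytes markers not assessed for first cohort" (SAP 4.3).
- Part A total: 4 × 8 = 32, which agrees with the protocol.
- Planned for leukocyte sampling: 3 × 8 = 24, of whom 3 × 6 = 18 are active and 3 × 2 = 6 placebo.
- One second-row active subject: 1/6 = 16.7% of the dose level and 1/18 = 5.6% of active subjects sampled.
- Two such subjects: 2/18 = 11.1% of active subjects sampled, and 2/6 = 33.3% of one dose level if both fall in it.
- Post-dose points per subject: T_Cmax, T_Cmax + 3 h, 12 h, 24 h, and 48 or 72 h, which makes 5. One subject therefore supplies up to 5 of 18 × 5 = 90 active points, again 5.6%.

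These are shares of planned counts. The documents do not allow an estimate of the effect on a slope or an Emax parameter.

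**The case against.** The best defence is that the analysis is a concentration-response correlation, so valid PK is essential and the PKS is a natural choice. That is half right: PK validity is necessary but not sufficient. What is missing is the PDS condition alongside it.

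A second defence is that the case should be rare and is partly handled elsewhere. Volunteers are healthy, restricted in recent medication and resident from D-1 to D4. Subjects may be withdrawn by agreement after taking a concomitant medicine (Protocol 5.3). Withdrawn subjects' data are evaluated only if the sponsor and the investigator agree that this is valid (Protocol 3.6). This lowers the likely frequency but does not cover a subject who completes the study with a deviation affecting pharmacodynamics only.

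A third is that little hangs on the result. Escalation decisions list safety and PK inputs (Protocol 3.3.3.2), and the escalation stopping rules use no pharmacodynamic marker (Protocol 3.5.4). That is correct, and it limits the weight of the point.

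A reader might also infer that naming the PKS is what keeps in a subject who had an infection or was given a permitted medicine. The documents do not support this. Protocol 5.3 says that "in case of intercurrent illness or emergency, the investigator is allowed to use any needed medication", so such use is not in itself a deviation. Both sets exclude only on major deviations, so for these subjects replacing one set by the other changes nothing.

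**Conclusion.** The mismatch stands: SAP 4.3 analyses the leukocyte markers in a set that does not screen for deviations affecting them, while the set that does so goes unused for any outcome. The consequence is confined to subjects with a major deviation affecting pharmacodynamics but not pharmacokinetics. Each such active subject is 16.7% of a dose level and 5.6% of the 18 active subjects planned for sampling, assuming full cohorts of 6 active and complete sampling. The number of such subjects is unknown and may be zero.

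This is a modest point about a secondary, exploratory analysis, and the safety and PK results do not depend on it.

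It is also tempting to conclude that the PDS should be widened to exclude intercurrent illness or permitted treatment after dosing. The documents give no sign of that intent. DF2755A inhibits neutrophil chemotaxis (Protocol 1.1), so an infection after dosing could be related to the drug, and removing it by judgement could bias the exposure-response picture.

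**What to change.** In the pharmacodynamic table of SAP 4.3, change the population from the PKS to subjects in both the PKS and the PDS. Leave the set definitions in SAP 2.4 as they are.

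The cost is one line of text and the matching selection in the program. No new data are needed, because SAP section 5 already lists membership of both sets by subject. Protocol 10.6 allows the plan to be revised, with a final plan issued before database lock. Settling the population by then also avoids choosing it after the marker data have been seen by treatment.
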